#### **4.1.1 General data reporting conventions**

Categorical data will be summarized by the number and percentage of subjects in each category. Percentages will be rounded to 1 decimal place. Continuous variables will be summarized by mean, median, standard deviation (SD), minimum, and maximum, unless stated otherwise. The mean and median will be presented with one more decimal place than the raw data. The standard deviation will be presented with two more decimal places than the raw data. Minimum and maximum values will have the same number of decimal places as the raw data.

Data collected at unscheduled visits will not be included in summaries by timepoint or visit unless stated otherwise. Data collected at unscheduled visits will be presented in listings.

In tables and listings, treatment group will be presented as ‘nirsevimab’.

#### **4.1.2 Definition of baseline**

Baseline will be defined as the last non-missing value prior to administration of nirsevimab, unless stated otherwise.

#### **4.1.3 Derivation of study day**

Study day will be calculated as follows:

- If the evaluation date is on or after the administration date of nirsevimab:

study day = date of evaluation – administration date of nirsevimab + 1

- If the evaluation date is before the administration date of nirsevimab:  
study day = date of evaluation – administration date of nirsevimab

#### **4.1.4 Handling of missing data**

No imputation for missing data will be applied except for the partial dates.

##### **4.1.4.1 General imputation rule for partial dates**

- Partial dates where only the year is known:
  - For start dates assume January 1st;
  - For stop dates assume December 31st.
- Partial dates where only the month and year are known:
  - For start dates assume the first of the month;
  - For stop dates assume the end of the month.

##### **4.1.4.2 Imputation rule for partial AE start date**

- When AE range is available:

Step 1: For partial AE start dates, regardless if only the year is known, or only the month and year are known, first use the following rule to impute AE start date:

- a. Assume (dose date + 1 day) if AE started  $\leq$  7 days after dosing;
- b. Assume (dose date + 7 days) if AE started 8 - 14 days after dosing;
- c. Assume (dose date + 14 days) if AE started  $>14$  days after dosing.

Step 2: After getting an imputed AE start date from Step 1, compare the imputed AE start date with the partial AE start date:

- If partial AE start date where only the year is known:
  - If the year of partial AE start date is the same as imputed AE start date from Step 1, then use imputed AE start date from Step 1;
  - If the year of partial AE start date is different from the year of imputed AE start date from Step 1, assume partial AE start date as January 1st;
  - If the imputed AE start date is after AE end date, then set AE start date the same as AE end date.
- If partial AE start date where only the year and month are known:
  - If the year and month of partial AE start date are the same as imputed AE start date from Step 1, then use imputed AE start date from Step 1;
  - Otherwise, assume partial AE start date as the first day of the month.
  - If the imputed AE start date is after AE end date, then set AE start date the same as AE end date.
- When AE range is not available:
  - If partial AE start date where only the year is known,
    - If the same year as dosing date:

- i. If AE does not occur on the same day of dosing, then AE start date is one day after dosing date;
- ii. Otherwise, AE start date is the same as dosing date.
- If different year from dosing date, assume January 1st.
- If partial AE start date where only the year and month are known,
  - If the same year and month as dosing date:
    - i. If AE does not occur on the same day of dosing, then AE start date is one day after dosing date;
    - ii. Otherwise, AE start date is the same as dosing date.
  - Otherwise, assume the first day of that month.

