5.5.1 Time Period for Collection of Adverse Events

AEs and SAEs will be collected from the time of signature of informed consent through Day 361.

AESIs and NOCDs will be collected from the time of dosing through Day 361.

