#### **3.1.1      Treatment-emergent adverse events and serious treatment-emergent adverse events (TEAEs and TESAEs)**

Treatment-emergent adverse events are defined as AEs whose onset occurs after receiving nirsevimab and within 360 days post dose. Adverse events with completely missing onset dates and a stop date after the start date of receiving nirsevimab (or unknown stop date) will also be considered treatment emergent. A TESAE is an TEAE which is serious.

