#### **4.1.4.3 Imputation rule for partial concomitant medications dates**

- If a concomitant medication is not associated with an AE:
  - a. Apply general imputation rule described in Section [4.1.4.1](#) wherever it fits.
- If a concomitant medication is associated with an AE:
  - a. The concomitant medication start date will be imputed with either observed or imputed AE start date described in Section [4.1.4.2](#). If there are multiple associated AEs, the earliest AE start date either observed or imputed will be used for imputation.
  - b. The concomitant medication end date will be imputed by the general imputation rule described in Section [4.1.4.1](#) for end date whenever fits. Then compare the imputed concomitant medication start date or end date with the data cut-off and apply the implementation rule for data cut-off for interim analysis described in Section [4.1.5](#). If the imputed concomitant medication end date is after the end of study date, then the concomitant medication end date will be replaced with the end of study date.

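### SAP 4.1.4.2: with no AE range, a partial start date in the dosing year or month is imputed to the day after dosing with no stop-date check, so an AE that ended before dosing can become a TEAE

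*SAP*

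**What the plan says.** SAP 4.1.4.2 has two branches.

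- **AE range available.** The start date is first imputed from one of three ranges, all after dosing (up to 7 days, 8 to 14 days, more than 14 days), and then compared with the known year or month. Both sub-branches end with the same safeguard: "If the imputed AE start date is after AE end date, then set AE start date the same as AE end date".
- **AE range not available.** If the known year (or year and month) is that of dosing: "If AE does not occur on the same day of dosing, then AE start date is one day after dosing date". For an AE on the dosing day: "Otherwise, AE start date is the same as dosing date". If the known period is not that of dosing, the date goes to the start of that period: "If different year from dosing date, assume January 1" for a year-only date, and "Otherwise, assume the first day of that month" for a year-month date. No line in this branch refers to the AE end date.

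SAP 3.1.1 decides treatment emergence by onset after dosing and within 360 days. It uses the stop date in one case only: "Adverse events with completely missing onset dates and a stop date after the start date of receiving nirsevimab (or unknown stop date") also count as treatment-emergent.

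Protocol 5.5.1 sets the collection period: "AEs and SAEs will be collected from the time of signature of informed consent through Day 361". Protocol Table 4 allows screening from Day -30 to Day -1. SAP 4.2.4.1 intends AEs that occur before dosing to appear only in a listing of non-treatment-emergent events.

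For a partially dated medication linked to an AE, SAP 4.1.4.3 says: "The concomitant medication start date will be imputed with either observed or imputed AE start date".

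**The concern.** A child can have an AE between consent and dosing that starts and stops before the injection. The listed ranges describe post-dose onset only, so such an AE would be expected to have no range and to fall into the branch without the end-date check. If its partial start date shares the dosing year, or the dosing year and month, the rule places onset on the day after dosing even when the recorded stop date shows the event was already over.

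The result conflicts with the SAP's own treatment of less complete data. With no start date at all and a stop date before dosing, the AE is not a TEAE; knowing the month or year of onset turns the same AE into one. SAP 4.2.4.1 states the intent to list pre-dose events separately, but gives no rule that overrides an imputed start date.

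Safety is the primary objective and there is no control arm, so no comparator rate carries the same misdating. The tables affected are the all-TEAE tables and the early-onset tables in SAP 4.2.4.5. The TEAE listing, which shows start, stop and duration, would contain a start later than its stop.

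**Working it through.** The plan gives no figure on this point to reproduce. The check applies the rules literally.

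**Inputs.** Imputation rules: SAP 4.1.4.2. Study day: SAP 4.1.3 (date minus dosing date, plus 1 on or after dosing). TEAE definition: SAP 3.1.1. Onset windows of study day ≤ 1, 3, 7 and 14: SAP 4.2.4.5. Screening window of up to 30 days: Protocol Table 4. About 100 subjects, about 50 per dose group: Protocol 3.1.1.

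**1. One record (dates assumed).** Dosing 20 Oct 2021; start recorded as October 2021, or as 2021 only; stop 12 Oct 2021; no range.

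| Rule applied | Start | Study day | TEAE? |
|---|---|---|---|
| No-range branch as written | 21 Oct | 21 − 20 + 1 = 2 | Yes |
| No-range branch plus end-date check | 12 Oct | 12 − 20 = −8 | No |
| Range branch, ≤ 7-day category | 12 Oct | −8 | No |
| Onset wholly missing (SAP 3.1.1) | none | – | No; stop is not after dosing |

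As written, the start is 21 − 12 = 9 days after the stop. Study day 2 falls within 3, 7 and 14 days, but not within 1 day.

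**2. Reach of the rule.** Take every dosing day in 2021 and every start/stop pair within Day -30 to Day -1, equally weighted. There are 1 + 2 + … + 30 = 465 pairs per dosing day, so 365 × 465 = 169,725 records, all ended before dosing. Records that become TEAEs:

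- Year-month start: 56,354 / 169,725 = 33%.
- Year-only start: 160,270 / 169,725 = 94%.
- Either type with the end-date check added: 0 / 169,725.

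These shares show how far the rule reaches once a record has a partial start and a pre-dose stop. They do not forecast event counts, because the documents do not say how often start dates are partial.

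**3. Effect on a table row.** Per affected child, at most 1/100 = 1.0 percentage point overall and 1/50 = 2.0 points in a dose group. These are maxima: SAP 4.2.4.1 counts a subject once per category, so a child already in the row adds nothing. As a yardstick only, the Phase 2b nirsevimab group (Protocol 1.4.3, healthy preterm infants) had 86.2% with any TEAE and 12.5% with one within 7 days. At those rates, and if misdated children were typical, the chance that a child is not already counted is 100 − 86.2 = 13.8% in the any-TEAE row and 100 − 12.5 = 87.5% in the 7-day row. The early-onset rows are therefore the more exposed.

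**4. Linked medication (dates assumed).** Same dosing and stop dates, AE start recorded as 2021 only, linked medication start recorded as September 2021. SAP 4.1.4.3 gives the medication a start of 21 Oct 2021, against its known month. With the end-date check added to the AE rule it becomes 12 Oct 2021, which still contradicts September. This needs its own line.

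**The case against.** The strongest reply is that several conditions must coincide: onset after consent but before dosing, a partial start date, a stop date known to precede dosing, a matching period, and no range. Screening and dosing may fall on the same day (Protocol Table 5, footnote a), which leaves little pre-dose window. Active infection, and fever or acute illness within 7 days before dosing, are exclusions (Protocol 4.1.3). A month-only stop in the dosing month is imputed to month end (SAP 4.1.4.1) and usually shows no conflict. Data validation and query handling are planned, and a start after its stop would be visible in the listing. All of this stands as an argument that few records are affected. None of it supplies the missing rule: a query may catch a record, but the written algorithm still misclassifies it.

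Imputing onset to the post-dose period is also a recognised conservative choice. That holds when timing is ambiguous; a stop date before dosing removes the ambiguity.

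Three stronger readings are tempting but unsupported.

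- A reader might infer that every partial date in this branch is pulled to dosing. It is not: dates outside the dosing year or month go to January 1 or the first of the month.
- A reader might infer that all tables read for reactions to the injection are distorted. The within-1-day table is not. AESIs and NOCDs are collected only from dosing, skin-reaction assessment covers post-dose reactions, and the causality guidance in Protocol Appendix A asks whether product had been received, so AESI, NOCD, skin-reaction and related-event outputs should be largely unaffected. TESAEs are not excluded by the rule, but 24-hour SAE reporting with follow-up makes a partial date unlikely.
- A reader might set two misdated children in 100 against the Phase 2b 12.5% and call it a 2 / 12.5 = 16% inflation. The count of two has no source in the documents, and the 12.5% comes from a different population.

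**Conclusion.** The rule is wrong as written for one defined set of records: no AE range, a partial start date in the dosing year or the dosing year and month, and a stop date known to be before dosing. Such an AE is classed as a TEAE at study day 2, contrary to the intent in SAP 4.2.4.1 and to the result SAP 3.1.1 gives when onset is wholly missing.

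The effect is bounded at 1 percentage point per affected child at n = 100, or 2 points at 50 per dose group, and is zero for a child already in that row. The group size of 50 is an assumption: the protocol plans about 50 per group by RSV season, while SAP 1.2 drops season from dose selection and gives no group sizes. The number of affected children is unknown and probably small. The direction is over-counting, so the misdating adds events to these tables and does not remove any.

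The finding also assumes that screening AEs carry no range. That is inferred from the three post-dose categories listed, because the eCRF is not in the documents. The point is a small defect in a primary safety derivation, worth correcting because the correction is already written elsewhere in the same section.

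**What to change.** In SAP 4.1.4.2, add to both parts of the branch without an AE range the line already used in the other branch: "If the imputed AE start date is after AE end date, then set AE start date the same as AE end date". In the same place or in SAP 3.1.1, state that an AE with a stop date before the dosing date is not treatment-emergent, whatever is known of its start.

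As a minor follow-on in SAP 4.1.4.3, use the linked AE's start date only where it agrees with the known year or month of the medication; otherwise apply the general rule in SAP 4.1.4.1. This touches listings and exploratory medication-use counts only.

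The cost is three sentences in the SAP and a small programming change. No new data are needed.

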#### **4.1.4.3 Imputation rule for partial concomitant medications dates**

- If a concomitant medication is not associated with an AE:
  - a. Apply general imputation rule described in Section [4.1.4.1](#) wherever it fits.
- If a concomitant medication is associated with an AE:
  - a. The concomitant medication start date will be imputed with either observed or imputed AE start date described in Section [4.1.4.2](#). If there are multiple associated AEs, the earliest AE start date either observed or imputed will be used for imputation.
  - b. The concomitant medication end date will be imputed by the general imputation rule described in Section [4.1.4.1](#) for end date whenever fits. Then compare the imputed concomitant medication start date or end date with the data cut-off and apply the implementation rule for data cut-off for interim analysis described in Section [4.1.5](#). If the imputed concomitant medication end date is after the end of study date, then the concomitant medication end date will be replaced with the end of study date.

#### **4.1.5 Implementation of data cut-off (DCO) for interim analysis**

The principle is to only report the data collected up to the DCO date (16May2022) for the interim analysis.

- Partial dates will be imputed before applying DCO.
- Records with start date after DCO will be removed in SDTM datasets
- If end date is after DCO, then end date will be reset as missing, event status will be reset as ongoing in SDTM datasets if applicable.

The date of DCO is displayed in the header of tables, listings and figures for DCO applied outputs as: ‘Interim Analysis: Data cut-off = 16MAY2022’. If outputs are produced before IA a prefix is added as ‘Pre-’.

#### **4.1.6 Character values of clinical laboratory variables**

Quantitative laboratory measurements reported as “ $< X$ ” or “ $\leq X$ ”, ie, below the lower limit of quantification, or “ $> X$ ” or “ $\geq X$ ”, ie, above the upper limit of quantification, will be converted

to half of X or X for the purpose of quantitative summaries, but will be presented as recorded, ie, as “< X” or “> X” in the listings.

For ADA titer reported as “< X” or “≤ X”, refer to Section 0 for details.

#### **4.1.7 Reporting PK concentration**

Individual compound concentrations below the lower limit of Quantification (LLOQ) of the assay are reported as NQ (not quantifiable) with the LLOQ defined in the Tables, Figures and Listings (TFLs).

For descriptive statistics:

- If, at a given time point, 50% or less of the plasma concentrations are not quantifiable (NQ), the geomean, coefficient of variation (CV), geoSD, arithmetic mean and standard deviation (SD) are calculated by substituting the limit of quantification (LOQ) for values which are NQ.
- If more than 50%, but not all, of the concentrations are NQ, the geomean, CV, geoSD, arithmetic mean, and SD are reported as not calculable (NC). The max value is reported from the individual data, and the min and median are set to NQ.
- If all the concentrations are NQ, the geomean and arithmetic mean are reported as NQ and the CV, geoSD and SD as NC.
- The number of values below LLOQ are reported for each time point along with the total number of collected values.

Three observations >LLOQ are required as a minimum for a plasma concentration to be summarized. Two values are presented as a minimum and maximum with the other summary statistics as NC.

For consistency, the same plasma concentration values are used in the mean data graphs as those given in the descriptive statistics summary table for each time point.

### **4.2 Analysis methods**

#### **4.2.1 Subject disposition and completion status**

A summary of subject eligibility, reasons for screen failure, reasons for early discontinuation and enrolment status as well as treatment received (including summary of subjects enrolled but not dosed) will be provided. In addition, disposition of subjects throughout the study, number of subjects who completed Day 151 for inclusion in the efficacy evaluation and number of subjects who completed the study (Day 361) as planned, will be provided. The

denominators for this summary will include all subjects who were enrolled and dosed unless stated otherwise. In addition, subjects who discontinued the study will also be listed.

Subjects enrolment will be presented by hemisphere, country, and site, with the date of first and last subjects IP administration, and the date last subject evaluated. This will be presented for the as-treated population only.

The number of subjects in the as-treated population and the as-treated Japan subpopulation will be provided.

#### **4.2.2 Demographic and baseline characteristics**

A summary of demographic information related to sex, ethnicity, race, age at IP administration (months) calculated from eCRF, age category at IP administration calculated from eCRF (age < 12 months, age  $\geq$  12 months), birth weight (kg), birth weight category (weight  $\leq$  2.5 kg, weight  $>$  2.5 kg), gestational age (weeks), multiple birth (yes/no), siblings enrolled in the study (yes/no), ever breastfed (yes/no), currently breastfed (yes/no), smokers in the household currently (yes/no), currently in day care (yes/no), weight (kg) on Day 1, weight category on Day 1 (weight  $<$  5 kg, weight  $\geq$  5 kg to  $<$  10 kg, weight  $\geq$  10 kg), subjects who met the subcategories of inclusion criteria 2 will be provided. Subjects will be excluded from the summary (eg, means and percentages) of an individual parameter if data are missing.

In addition, a summary of family history of atopy (including asthma, hay fever, eczema, wheezing) will be provided.

#### **4.2.3 Study drug exposure and treatment compliance**

Due to the simplicity of dosing for this study, exposure is summarized in the Subject Disposition table under “Subjects enrolled and dosed”.

Treatment compliance will be presented by the number and percentage of subjects who have received a full dose of nirsevimab. For subjects who did not receive a full dose of nirsevimab, the number and percentage of subjects who received  $>$  50% of full dose, 50% of full dose and  $<$  50% of full dose will also be provided.

#### **4.2.4 Primary analyses**

Treatment-emergent AEs, TESAEs, AESIs, skin reactions, and NOCDs will be summarized using descriptive statistics.

No safety data will be imputed. The handling of partial dates for AEs is described in Section 4.1.4.2.

#### **4.2.4.1 Treatment-emergent adverse events and treatment-emergent serious adverse events (TEAEs and TESAEs)**

Adverse events will be coded by MedDRA, Version 24.1 or higher.

The number and percentage of subjects with TEAEs in any category; TESAEs in any category; IP related TEAEs; IP related TESAEs; TEAEs with  $\geq$  grade 3 severity; TESAEs with  $\geq$  grade 3 severity; IP related TEAEs with  $\geq$  grade 3 severity; IP related TESAEs with  $\geq$  grade 3 severity; TEAEs with outcome of death; AESIs based on investigator assessment; IP related AESIs based on investigator assessment; AESI based on selected MedDRA PT codes; IP related AESIs based on selected MedDRA PT codes; NOCDs; IP related NOCDs; skin reactions; and IP related skin reactions; skin hypersensitivity reactions; and IP related skin hypersensitivity reactions will be provided. In the count of subjects with TEAEs, subjects with multiple events in the same category will be counted only once in that category. In addition, if the same AE occurs multiple times within a particular subject, the highest severity and level of relationship observed will be reported.

Adverse events with outcome of death can be identified in the ‘Adverse Events’ eCRF page, when “Outcome of AE” is flagged as ‘Fatal’. Other parameters such as “Serious”, “AE toxicity grade”, “Relationship, investigational product”, “Adverse event of special interest” (based on investigator assessment), “NOCD”, and “Skin reaction” can also be identified in the same ‘Adverse Events’ eCRF page.

All TEAEs and TESAEs will be provided by the number and percentage of subjects with the categorization by MedDRA system organ class (SOC) and preferred term (PT), the total number of TEAEs and TESAEs will also be provided. Key information such as subject identifier, sex, age, country, TEAE with SOC and PT, start and stop date of TEAE, duration of TEAE, TESAE and type of TESAE, outcome of TEAE, action taken with nirsevimab and causality to nirsevimab, will be listed for subjects with TEAEs.

The number and percentage of subjects with TEAEs, as well as categorization by MedDRA SOC and PT, and the highest severity will be provided.

The number and percentage of subjects with IP related TEAEs and TESAEs, as well as categorization by MedDRA SOC and PT will be provided.

The number and percentage of subjects with TEAEs with outcome of death, as well as categorization by MedDRA SOC and PT will be provided. Key information similar to those mentioned above will be listed for subjects with outcome of death.

Non-treatment-emergent AEs/ SAEs, defined as AEs/SAEs that occur prior to administration of nirsevimab or after Day 361, will be presented in an AE listing.

